6.6 Laboratory, Biomarker, and Other Biological Samples

"Local" laboratory tests may be performed either at a local certified laboratory or at the study site. "Central" laboratory tests should be drawn at the study site and may be analyzed at the coordinating center or sent to Roche.

6.6.1 Local laboratory assessments

Local laboratory assessments may include the following:

- Hematology (CBC, including RBC count, hemoglobin, hematocrit, WBC count with differential [neutrophils, eosinophils, lymphocytes, monocytes, basophils, and other cells], and platelet count)

- Serum chemistries including: sodium, potassium, chloride, bicarbonate, BUN, creatinine, glucose, calcium, magnesium, phosphorus, total bilirubin, ALT, AST,
- alkaline phosphatase, total protein, albumin and LDH
- C-reactive protein (CRP)
- Serum pregnancy test (only for women of childbearing potential, including premenopausal women who have had a tubal ligation)
- Urinalysis (specific gravity, pH, glucose, protein, ketones, and blood)
- Thyroid function testing (thyroid-stimulating hormone [TSH], free T3, free T4)
- HBV serology (HBsAg, antibodies against HBsAg, hepatitis B core antigen)
- HBV DNA should be obtained prior to Cycle 1, Day 1 if patient has positive serology for anti-HBc Ab.
- HCV serology (anti-HCV antibody)
- HIV testing (if in accordance with national and/or institutional guidelines)
- The following laboratory tests will be performed **only** if there is clinical suspicion of acute immune-related toxicity. These should be performed at any point during the study if immune-related toxicity is suspected:
 - Auto-antibody testing
 - Anti-nuclear antibody (ANA)
 - Anti-double-stranded DNA (Anti-dsDNA)
 - Circulating anti-neutrophil cytoplasmic antibody (C-ANCA)
 - Perinuclear anti-neutrophil cytoplasmic antibody (P-ANCA)
 - Epstein-Barr virus (EBV) serology
 - Creatine kinase (CK) level

6.6.2 Central laboratory assessments

Central laboratories will coordinate the collection of archival tumor, fresh tumor, and leftover tumor tissue and blood samples for the assessment of atezolizumab and tiragolumab biomarkers, ATA assays, and auto-antibody testing. Instruction manuals and supply kits will be provided for all central laboratory assessments.

The following assessments will be performed at a central laboratory or Genentech:

- Anti-Therapeutic Antibody (ATA) assays and atezolizumab and tiragolumab levels (only in case of clinical suspicion of serious acute immune or inflammatory toxicity, related to atezolizumab and/or tiragolumab)
 - Serum samples will be assayed for the presence of ATAs to anti-atezolizumab and tiragolumab with use of validated

immunoassays. Atezolizumab and tiragolumab levels will be assessed using validated assays.

- T, B, and NK cell (TBNK) assays
- PD-L1 testing by IHC
 - Archival tissue blocks are slides will be shipped to a central lab for analysis of PD- L1 expression by IHC
- Biomarkers in tumor tissues
- RNA and DNA will be extracted from ~ 5 7 μ sections for the analysis of genes associated with tumor immune biology as well as genomic mutations.
- Biomarker and immunologic assays in blood samples
 - Blood samples will be obtained for biomarker evaluation from all eligible patients at screening, before treatment, on treatment, at the treatment discontinuation visit, and in the follow-up period. Samples will be processed to obtain blood cells (and their derivatives), plasma, and serum for the determination of changes in surrogate biomarkers and immunologic assays that may be altered in UC or biomarkers that are related to UC and tumor immune biology (including but not limited to IFN-gamma and other exploratory biomarkers).
- Biomarker immunologic assays in urine samples
 - Urine samples will be obtained for biomarker evaluation from all eligible patients before study treatment, on treatment, and at the treatment discontinuation visit. Samples will be processed to obtain tumor cells (and their derivatives) and immune cells, for the determination of changes in surrogate biomarkers that may be altered in UC or biomarkers that are related to UC and tumor immune biology (including but not limited to IFN-gamma and other exploratory biomarkers).

Any remaining samples collected for biomarker assays, may be used for exploratory biomarker profiling and identification purposes as appropriate. In addition, exploratory biomarkers (including but not limited to markers related to immune or UBC biology) may be evaluated in tissue samples.

- Archival and fresh tumor tissue sample
 - Representative tumor specimens in paraffin blocks (preferred) or at least 15 unstained slides, with an associated pathology report, should be submitted prior to study enrollment.
 - Tumor tissue should be of good quality based on total and viable tumor content (sites will be informed if the quality of the submitted specimen is inadequate to determine tumor PD-L1 status). Fine-needle aspiration, brushing, cell pellets, and lavage samples are not acceptable. For any core needle biopsy specimens, at least three cores should be submitted for evaluation.

- Additional archival tumor specimens should be submitted if available.
- Any fresh and/or paraffin embedded TURBT specimens (prior to study therapy or while on study therapy) or cystectomy specimens (after study therapy) will be made available for assessment of tumor response, and characterization of PD-1 and PD-L1 expression and of immunologic infiltrate.
- For archival samples, the remaining tumor tissue block for all patients enrolled will be returned to the site upon request or 18 months after final closure of the study database, whichever is sooner. Tissue samples from patients who are not eligible to enroll in the study will be returned no later than 4 weeks after eligibility determination.
- Tumor biopsy at the time of initial radiographic recurrence
 - All patients will undergo a mandatory tumor biopsy sample collection, if clinically feasible as determined by the study investigator in consenting patients, at the first evidence of radiographic disease recurrence. Subjects may opt-out of this biopsy.
 - Acceptable samples include core needle biopsies for deep tumor tissue or lymph nodes or excisional, incisional, punch, or forceps biopsies for cutaneous, subcutaneous, or mucosal lesions. For core needle biopsy specimens, at least three cores should be submitted for evaluation. A fine needle aspirate is not acceptable.
- Use and storage of remaining samples from study-related procedures
 - The remainder of samples obtained for study-related procedures will be destroyed no later than 5 years after the end of the study or earlier depending on local regulations.

Please refer to the laboratory manual for additional details on laboratory assessments and sample handling.

6.7 Cardiac Tests: Electrocardiograms (ECGs)

Twelve-lead ECG is required at screening and as clinically indicated. ECGs should be obtained on the same machine whenever possible. Lead placement should be as consistent as possible. ECG recordings should be performed after the patient has been resting in a supine position.

For safety monitoring purposes, the investigator must review, sign, and date all ECG tracings. Paper copies of ECG tracings will be kept as part of the patient's permanent study file at the site. Any morphologic waveform changes or other ECG abnormalities must be documented on the eCRF.

6.8 Anti-Therapeutic Antibody and atezolizumab and tiragolumab Testing

Atezolizumab and/or tiragolumab may elicit an immune response. Patients with signs of any potential immune response to atezolizumab and/or tiragolumab will be closely monitored.

Validated assays will be employed to detect ATAs and atezolizumab and/or tiragolumab levels if warranted based on clinical suspicion of ATA development.

6.9 Study Schedule

6.9.1 Screening

The Screening procedures and assessments must be completed **within 28 days** of the Day 1 Visit. Local and Central laboratory assessments done within 14 days of beginning treatment do not need to be repeated for Cycle 1 Day 1.

- Physical examination
- Vital signs
- Complete medical history
- Baseline conditions assessment
- Documentation of disease
- Performance status
- History of prior treatments and any residual toxicity relating to prior treatment
- Baseline medications taken within 7 days of Day 1
- Archival sample of tumor tissue acquisition. Acquisition of representative formalin-fixed paraffin-embedded (FFPE) tumor specimens in paraffin blocks (blocks preferred) or at least 15 unstained slides, with an associated pathology report, for central testing for tumor PD-L1 expression and immune characterization.
- Laboratory assessments:
 - Hematology (CBC, including RBC count, hemoglobin, hematocrit, WBC count with differential [neutrophils, eosinophils, lymphocytes, monocytes, basophils, and other cells], and platelet count)
 - Serum chemistries including: sodium, potassium, chloride, bicarbonate, BUN, creatinine, glucose, calcium, magnesium, phosphorus, total bilirubin, ALT, AST, alkaline phosphatase, total protein, albumin and LDH
 - C-reactive protein (CRP)
 - Serum pregnancy test (only for women of childbearing potential, including premenopausal women who have had a tubal ligation) **must be performed within 14 days of cycle 1 day 1.**
 - Urinalysis (specific gravity, pH, glucose, protein, ketones, and blood)
 - Thyroid function testing (thyroid-stimulating hormone [TSH], free T3, free T4)
 - HBV serology (HBsAg, antibodies against HBsAg, hepatitis B core antigen)

- HBV DNA should be obtained prior to Cycle 1, Day 1 if patient has positive serology for anti-HBc Ab.
- HCV serology (anti-HCV antibody)
- HIV testing (if in accordance with national and/or institutional guidelines)
- Serum will be banked and frozen during screening for the following assays in all patients, however these assays will only be run to establish baseline values *if there is clinical suspicion of acute immune-related toxicity related to atezolizumab and/or tiragolumab:*
 - Auto-antibody testing, including ANA, Anti-dsDNA, C-ANCA, P-ANCA
- EBV serology (See Section 3.3.2 Exclusion Criteria)
- Creatine kinase (CK) level
- Central laboratory assessments
 - TBNK blood sample
 - Urine sample for cytokine assessment.
- Imaging (CT or MRI) of the chest, abdomen, and pelvis for tumor/lesion assessment. These assessments may be performed up to **45 days** prior to study entry. Imaging of the upper tracts with an intravenous pyelogram, CT urography, renal ultrasound with retrograde pyelogram, ureteroscopy, or MRI urogram should be performed if clinically indicated.
- Electrocardiogram (ECG)
- Bone scan (technetium OR sodium-fluoride PET/CT) (only for subjects with an elevated alkaline phosphatase or clinical suspicion of bony metastatic disease)

6.9.2 Treatment Period

Day 1 of all cycles (+/- 3 days for cycles ≥ 2)

- Physical examination
- Vital signs
- Performance status
- Evaluation of adverse events
- Concomitant medications
- Local laboratory assessments. Unless otherwise noted, they may be obtained up to 96 hours prior to day 1 of each cycle:
 - CBC with differential and platelet count

- Blood chemistry assessment, including: sodium, potassium, chloride, bicarbonate, BUN, creatinine, glucose, calcium, magnesium, phosphorus, total bilirubin, ALT,
- AST, alkaline phosphatase, total protein, albumin and LDH
- C-reactive protein
- Urinalysis
- Central laboratory assessments
 - Immunologic and pharmacodynamic evaluations
 - TBNK blood sample
 - Plasma, serum, and blood sample for PD biomarkers
 - Urine sample for cytokine assessment.
- Atezolizumab/tiragolumab infusion. See section 5.1 for dosing and administration requirement.

6.9.3 End of Treatment (prior to cystectomy)

To be completed within 30 days of the last dose of study drug and prior to cystectomy.

- Physical examination
- Vital signs
- Performance Status
- Evaluation of adverse events
- Concomitant medications
- Local Laboratory Assessments. Unless otherwise noted, they may be obtained up to 96 hours prior to the visit:
 - Hematology assessment, including CBC with differential and platelet count
 - Blood chemistry assessment, including: glucose, BUN, creatinine, sodium, potassium, magnesium, chloride, bicarbonate, calcium, phosphorus, total bilirubin, ALT, AST, alkaline phosphatase, LDH, total protein, and albumin
 - C-reactive protein
 - Urinalysis
 - TSH, T3 and T4
- Central laboratory assessments
 - Immunologic and pharmacodynamic evaluations
 - TBNK blood sample
 - Plasma, serum, and blood sample for PD biomarkers
 - Urine sample for cytokine assessment.
- Imaging (CT or MRI) of the abdomen, and pelvis for tumor/lesion assessment, and if clinically indicated, imaging of the chest (CXR or CT).

Imaging of the upper tracts with an intravenous pyelogram, CT urography, renal ultrasound with retrograde pyelogram, ureteroscopy, or MRI urogram should be performed if clinically indicated.

- No repeat TURBT is required after the initiation of study therapy, however if performed per institutional standard of care then any tissue or other tumor biopsy should be obtained for analysis.

6.9.4 Post-cystectomy/Follow Up Visits

Patients will be followed every 4 weeks (+/- 1 weeks) from the time of cystectomy for 12 weeks, and thereafter every 12 weeks for up to 2 years after cystectomy or until disease progression, death, study termination, or withdrawal from study, whichever occurs first.

- Radiographic imaging should occur every 12 weeks and at end of treatment as outlined in the study calendar.
- The following Central Laboratory tests should be obtained every 12 weeks
 - TBNK blood sample
 - Plasma, serum, and blood sample for PD biomarkers
 - Urine sample for cytokine assessment.

Once all therapy is completed patients should be followed every 12 weeks until the completion of 2 years after cystectomy or until disease progression, death, study termination, or withdrawal from study, whichever occurs first.

Patients who discontinue study treatment prior to cystectomy for reasons other than disease progression (e.g., toxicity) should continue to undergo scheduled tumor assessments until the patient dies, experiences disease progression, withdraws consent, for 2 years from the last dose of study therapy or until the study closes, whichever occurs first.

Patients who start a new anti-cancer therapy (i.e. adjuvant chemotherapy) in the absence of disease progression should continue to be followed for progression according to the protocol schedule of response assessments unless they withdraw consent, experience disease progression, death, study termination, or withdrawal from study, whichever occurs first.

In addition to tests performed per local standard of care, the following procedures will be performed at the Follow Up Visit(s):

- Physical examination
- Vital signs
- Performance Status
- Evaluation of adverse events
 - After initiation of study drug, all adverse events will be reported until 30 days after the last dose of study treatment. After this period, investigators should report any deaths, serious adverse events, or other adverse events of concern that are believed to be related to prior treatment with study drug.
- Concomitant medications

- Pathologic review of tumor response (first follow up visit only)
- Local Laboratory Assessments. Unless otherwise noted, they may be obtained up to 96 hours prior to the visit:
 - Hematology assessment, including CBC with differential and platelet count
 - Blood chemistry assessment, including: glucose, BUN, creatinine, sodium, potassium, magnesium, chloride, bicarbonate, calcium, phosphorus, total bilirubin,
 - ALT, AST, alkaline phosphatase, LDH, total protein, and albumin
 - C-reactive protein
 - Urinalysis including urine cytology
 - TSH, T3 and T4
- Central laboratory assessments
 - Immunologic and pharmacodynamic evaluations
 - TBNK blood sample
 - Plasma, serum, and blood sample for PD biomarkers
 - Acquisition of cystectomy tissue (either fresh or paraffin embedded) for immunologic characterization.
- Imaging
 - CT or MRI of the abdomen and pelvis for tumor recurrence to be performed every 12 weeks.
 - Imaging of the upper tracts with an intravenous pyelogram, CT urography, renal ultrasound with retrograde pyelogram, ureteroscopy, or MRI urogram should be performed per institutional standard of care.
 - Chest imaging (Chest X-ray or CT Chest) every 12 weeks.
- Tumor tissue (only at the first evidence of radiographic disease recurrence)
 - Mandatory tumor biopsy sample collection, if clinically feasible as determined by the study investigator in consenting patients. Subjects may opt-out of this biopsy.
 - Acceptable samples include core needle biopsies for deep tumor tissue or lymph nodes or excisional, incisional, punch, or forceps biopsies for cutaneous, subcutaneous, or mucosal lesions. For core needle biopsy specimens, at least three cores should be submitted for evaluation. A fine needle aspirate is not acceptable.

6.9.5 End of Study Visit

In addition to tests performed per local standard of care, at 1 month (allowed up to 2 months) off study the following procedures will be performed at the End of Study Visit:

- Physical examination

- Vital signs
- Performance Status
- Evaluation of adverse events
 - After initiation of study drug, all adverse events will be reported until 30 days after the last dose of study treatment. After this period, investigators should report any deaths, serious adverse events, or other adverse events of concern that are believed to be related to prior treatment with study drug.
- Concomitant medications
- Pathologic review of tumor response (if not already performed)
- Local Laboratory Assessments. Unless otherwise noted, they may be obtained up to 96 hours prior to the visit:
 - Hematology assessment, including CBC with differential and platelet count
 - Blood chemistry assessment, including: glucose, BUN, creatinine, sodium, potassium, magnesium, chloride, bicarbonate, calcium, phosphorus, total bilirubin,
 - ALT, AST, alkaline phosphatase, LDH, total protein, and albumin
 - C-reactive protein
 - Urinalysis including urine cytology
- Central laboratory assessments
 - Immunologic and pharmacodynamic evaluations
 - TBNK blood sample
 - Plasma, serum, and blood sample for PD biomarkers
 - Acquisition of cystectomy tissue (either fresh or paraffin embedded) for immunologic characterization (if not done already performed)
- Imaging (only required if not performed within the last 8 weeks)
 - CT or MRI of the abdomen and pelvis
 - Imaging of the upper tracts with an intravenous pyelogram, CT urography, renal ultrasound with retrograde pyelogram, ureteroscopy, or MRI urogram should be performed per institutional standard of care.
 - Chest imaging (Chest X-ray or CT Chest)
- Tumor tissue (only at the first evidence of radiographic disease recurrence, if not already performed)
 - Mandatory tumor biopsy sample collection, if clinically feasible as determined by the study investigator in consenting patients. Subjects may opt-out of this biopsy.
 - Acceptable samples include core needle biopsies for deep tumor tissue or lymph nodes or excisional, incisional, punch, or forceps

biopsies for cutaneous, subcutaneous, or mucosal lesions. For core needle biopsy specimens, at least three cores should be submitted for evaluation. A fine needle aspirate is not acceptable.

6.9.6 Long Term/Survival Follow-up Procedures

Following early discontinuation all patients will be followed for 2 year relapse free survival and subsequent anti-cancer therapy. Survival and subsequent anti-cancer therapy follow-up information will be collected via telephone calls, patient medical records, and/or clinic visits approximately every 3 months until death, loss to follow-up, withdrawal of consent, or study termination by the Sponsor, for up to 2 years after cystectomy. Subjects will not be followed for overall survival.

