2.2 Secondary Objective(s) and Endpoint(s)

Cohorts A and B

Multi-Dose Cohorts

1. To evaluate the safety and feasibility of administering up to 3 cycles of Atezolizumab pre-operatively to patients with resectable urothelial bladder cancer. Note this is the coprimary objective for Cohort B.
 - Endpoint: The percentage of patients with treatment-related adverse events according to CTCAE v5.0 or treatment-related delays in surgery beyond 12 weeks following administration of neoadjuvant treatment with atezolizumab with or without tiragolumab. Note for Cohort A CTCAE v4.0 was used.

Expansion Cohorts

1. To assess the anti-tumor activity of neoadjuvant treatment as determined by pathologic partial response (<pT2N0) assessed at the time of radical cystectomy
 - Endpoint: Percentage of patients with pathologic downstaging (<pT2N0) at the time of radical cystectomy
2. To determine the 2-year relapse-free survival (RFS) rate and median RFS from time of radical cystectomy in patients treated with neoadjuvant therapy
 - Endpoint: 2-year RFS rate and median RFS in ITT population
3. To determine the 2-year overall survival (OS) and median OS from time of radical cystectomy in patients treated with neoadjuvant therapy
 - Endpoint: 2-year OS rate and median OS in ITT population
4. To assess the intratumoral immune response of neoadjuvant by comparing pre-treatment TURBT with post-treatment cystectomy tumor specimens

- Endpoint: Association of tumor and T-cell PD-L1/PD-1 immunohistochemical expression with disease response

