- j. All measurable and evaluable lesions should be assessed and documented at the screening visit. The same radiographic procedure should be used throughout the study for each patient. Available results must be reviewed by the investigator before dosing at the next cycle. Pathologic review of tumor response should occur at the first follow up visit after cystectomy. Patients will undergo assessments for tumor recurrence every 12 weeks (+/- 2 weeks) for the first 2 years following cystectomy. Patients who discontinue from the initial treatment stage for reasons other than disease progression (e.g. toxicity) will continue scheduled tumor assessments until disease recurrence, withdrawal of consent, or death. Patients who start a new anti-cancer therapy in the absence of disease recurrence (e.g. adjuvant therapy) should be followed according to the protocol schedule unless they withdraw consent. Investigators may perform additional scans or more frequent assessments if clinically indicated.
- k. Tumor biopsy at recurrence, preferably at the time of radiographic progression. Patients may opt out of this biopsy. Acceptable samples include core needle biopsies for deep tumor tissue or lymph nodes or excisional, incisional, punch, or forceps biopsies for cutaneous, subcutaneous, or mucosal lesions. For core needle biopsy specimens, at least three cores should be submitted for evaluation.
- l. Survival follow-up information will be collected via telephone calls, patient medical records, and/or clinic visits approximately every 3 months until death, loss to follow-up, withdrawal of consent, or study termination by Sponsor. All patients will be followed for survival and new anti-cancer therapy information unless the patient requests to be withdrawn from follow-up; this request must be documented in the source documents and signed by the investigator. If the patient withdraws from study treatment but not from follow-up, the study staff may use a public information source (e.g., county records) to obtain information about survival status only.
- m. Hematology consists of CBC, including RBC count, hemoglobin, hematocrit, WBC count with automated differential (neutrophils, lymphocytes, eosinophils, monocytes, basophils, and other cells), and platelet count. A manual differential can be done if clinically indicated.

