8.3.3 Analysis of Secondary Endpoints

8.3.3.1 Near complete pathologic response rate, 2 year relapse-free survival, 2 year overall survival

Point estimates and 95% confidence intervals of the near complete pathologic response rate, defined as the presence of only pTa or pTis in patients with T2 or greater disease at baseline, the 2 year RFS rate defined from study start until recurrence of disease or death from any cause, and the 2 year overall survival (OS) rate defined from study start until death from any cause, will be obtained for patients enrolled in the study, and compared with the null hypothesis rate (see Section 8.1) separately by using one-sample proportion test. RFS and OS will be obtained by Kaplan Meier method for the ITT population.

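### Section 6.9.6 contradicts itself, calendar footnote l and the overall survival endpoint, so whether deaths after relapse are captured depends on which text a site follows

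*Combined protocol and SAP*

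**What the plan says.** OS is a listed secondary endpoint for the expansion cohorts. Section 2.2 gives the objective as "To determine the 2-year overall survival (OS) and median OS from time of radical cystectomy in patients treated with neoadjuvant therapy", with "Endpoint: 2-year OS rate and median OS in ITT population". Section 8.3.3.1 repeats it with another time origin, "the 2 year overall survival (OS) rate defined from study start until death from any cause", and names the estimator: "RFS and OS will be obtained by Kaplan Meier method for the ITT population".

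Four places say how deaths would come to be known:

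- Section 6.9.4 (clinic visits): after the first 12 weeks, visits run "every 12 weeks for up to 2 years after cystectomy or until disease progression, death, study termination, or withdrawal from study, whichever occurs first".
- Section 6.9.6 (survival follow-up): the section opens by addressing patients who discontinue early. It then says "Survival and subsequent anti-cancer therapy follow-up information will be collected via telephone calls, patient medical records, and/or clinic visits approximately every 3 months until death", with a limit of 2 years after cystectomy.
- Section 6.9.6, last sentence: "Subjects will not be followed for overall survival".
- Section 6.10, footnote l: "All patients will be followed for survival and new anti-cancer therapy information unless the patient requests to be withdrawn from follow-up". It also allows public records to be used for survival status when a patient has left treatment but not follow-up. The calendar has a matching survival row at Follow-Up and Off Study.

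**The concern.** An endpoint cannot be reported if the section on survival follow-up tells sites not to collect it. The sentence also falls where it does most harm. Clinic visits already end at progression, so telephone and record contact is the only route by which a death after relapse would be learned. Routine safety reporting is not a dependable back-up: under Section 7.4, more than 30 days after the last dose only serious events attributed to study treatment need be reported, and a death from relapsed cancer would not normally be one.

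A patient lost to contact at relapse is about to face a much higher risk of death than those who remain at risk. Censoring there breaks the Kaplan-Meier assumption. The curve then estimates something close to survival free of death without relapse, which is higher than OS. If sites followed different texts, their survival data would also not be comparable.

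**Working it through.** **1. Is there a figure in the plan to reproduce?** No. The documents state no expected OS, OS null value, event count or relapse rate. Cohort B's 21 patients are sized on the pT0 rate (Section 8.1). Any size for this point therefore rests on assumptions.

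**2. What each text implies for a patient who has cystectomy and then relapses within 2 years**

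| Text followed | Survival contact after relapse? |
|---|---|
| 6.9.4 alone | No; clinic visits have ended |
| 6.9.6, contact sentence | Yes, about every 3 months until death, to 2 years after cystectomy, if the section applies to this patient despite its opening words |
| 6.9.6, last sentence | No |
| Footnote l and its calendar row | Yes, all patients, no stop at progression and no 2-year limit |

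Two texts give contact, one denies it, and one is silent outside the clinic. For a dosed patient who never has cystectomy, the limit in 6.9.6 has no starting date.

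**3. Size if contact stops at relapse.** Illness-death model with constant hazards and T = 24 months. Assumptions, none from the documents:

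- R, 2-year relapse probability: 30-50%
- D, 2-year probability of death without relapse: 5-10%
- m, median survival after relapse: 10-14 months

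R and D are read as net probabilities. Hazards: a = -ln(1-R)/24, d = -ln(1-D)/24, u = ln2/m, and L = a + d.

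- Alive without relapse: S0 = (1-R)(1-D)
- Alive after relapse: S1 = a(e^(-24u) - S0)/(L - u)
- True 2-year OS = S0 + S1
- Kaplan-Meier with everyone censored at relapse tends to 1 - D
- Deaths seen = (d/L)(1 - S0); share missed = 1 - seen/(1 - OS)

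Worked corner with the smallest share missed (R 30%, D 10%, m 14): a = 0.01486, d = 0.00439, u = 0.04951, S0 = 0.630. S1 = 0.01486 x (0.305 - 0.630)/(0.01925 - 0.04951) = 0.160. OS = 0.790. Seen = 0.228 x 0.370 = 0.084. Missed = 1 - 0.084/0.210 = 60%.

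| R, D, m | True OS | Kaplan-Meier | Overstatement (points) | Deaths missed |
|---|---|---|---|---|
| 30%, 10%, 14 | 79.0% | 90% | 11.0 | 60% |
| 30%, 5%, 14 | 83.0% | 95% | 12.0 | 75% |
| 40%, 7.5%, 12 | 75.0% | 92.5% | 17.5 | 76% |
| 50%, 10%, 10 | 65.9% | 90% | 24.1 | 79% |
| 50%, 5%, 10 | 69.0% | 95% | 26.0 | 88% |

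Over the grid, true OS is 66-83%, the estimate 90-95%, and 60-88% of deaths are missed. In the middle row, 21 patients would have about 21 x 0.250 = 5.2 deaths, of which about 21 x 0.059 = 1.2 would be seen.

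**4. Sensitivity.** A simulation of the same type on wider assumptions (2-year RFS 50-70%, deaths without relapse 10-30% of RFS events, median survival after relapse 6-18 months) gives an overstatement of 6.6 to 30.2 points and 46-86% of deaths missed.

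**5. Size if footnote l is followed.** Nobody is censored at relapse, so the bias from this source is 0 points.

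**The case against.** The strongest reply is that the plan does provide for survival follow-up. The sentence just before the disputed one collects survival information until death with no stop at progression. Footnote l covers all patients and the calendar carries the row. Section 6.9.4 ends clinic visits, which are a separate activity from telephone and record contact, and nothing in the analysis section censors OS at relapse. The disputed sentence might even mean only that OS is not followed beyond the 2 years just stated, which would leave the 2-year rate intact.

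Much of this stands. A reader might infer from the last sentence of 6.9.6 that most deaths will be missed and 2-year OS will be overstated. The documents do not support that: it follows only where a site obeys that sentence over the other texts. Even then, whether most deaths are lost depends on rates the documents do not give, as the 46% lower end of the wider range shows.

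A reader might also infer that median OS is unattainable because contact stops at 2 years. That limit is in 6.9.6 but not in footnote l, and a median can be reported as not reached. The 46 and 77 months in Section 1.2 are weak benchmarks: 46 is the surgery-alone arm, and both come from a cisplatin-based chemotherapy trial, whereas this trial enrols patients who are ineligible for or decline cisplatin.

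What does not stand is that the other texts settle the matter. The benign reading of the last sentence is not what it says, the opening of 6.9.6 leaves unclear whether it covers patients who completed treatment and surgery, and the contradiction lies in the section that sites would consult for survival follow-up.

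**Conclusion.** The contradiction is certain and rests on the text alone: an OS endpoint, two passages that provide for survival contact, and one sentence that rules it out. The consequence is conditional. If a site follows the last sentence of 6.9.6, the bias is upward: about 11 to 26 points on 2-year OS on the main assumptions, and about 7 to 30 on the wider ones, with constant hazards and no death after relapse captured. If footnote l is followed, it is zero. OS is a secondary endpoint with no power claim, so the primary pT0 analysis is unaffected. The wording still needs correcting, because deaths not collected prospectively may be hard to recover later. Median OS is not a separate error; the 2-year limit in 6.9.6 simply has to be reconciled with footnote l, which has none.

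**What to change.** - Delete the last sentence of Section 6.9.6 and widen its opening so that it covers all dosed patients.
- State in Sections 6.9.4 and 6.9.6, in line with footnote l, that survival status is collected about every 3 months in every dosed patient, including after progression, after new therapy and where no cystectomy took place, through 2 years from the OS time origin.
- Choose one OS time origin. Section 2.2 uses cystectomy and Section 8.3.3.1 uses study start; a cystectomy origin leaves out patients who never have surgery.
- Add to Section 8.3.3.1 that OS is censored only at the date last known alive, never at relapse, and that the median is reported as not reached where that applies.
- Give 6.9.6 and footnote l the same end of follow-up.
- If survival follow-up is not intended, remove OS from the objectives and from Section 8.3.3.1 instead, and correct footnote l and the calendar row.

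The cost is a wording amendment. The extra work is a few telephone or record checks per relapsed patient, which footnote l already requires.
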